Hypothesis 1.6 (secondary): Those assigned to placebo will have a higher rate of cotinine-verified, seven-day point-prevalence nicotine vaping abstinence at end of treatment compared to EUC.

Hypothesis 1.7 (exploratory): Those assigned to varenicline will have an earlier onset of abstinence, longer latency to first lapse, longer latency to relapse, longer duration of abstinence, and greater total number of days of vaping abstinence than those assigned to placebo or EUC as

determined by using data ascertained daily with the emocha Mobile Health app (emocha) or REDCap surveys.

Aim 2 (secondary): To establish the safety and tolerability of varenicline in adolescents attempting to quit vaping nicotine.

Hypothesis 2.1: Nicotine withdrawal symptoms, craving, and negative mood symptoms will be less frequent and severe in the varenicline group than the placebo or EUCgroups.

Hypothesis 2.2: Those assigned to varenicline will have no greater incidence or severity of adverse events (AE) compared with those assigned to placebo or EUC during treatment and follow-up.

Aim 3 (exploratory): To assess if there are between group differences in consumption of alcohol, combusted tobacco, cannabis, and non-medical prescription drugs during the treatment and follow-up periods.

Exploratory Hypothesis: Those assigned to varenicline will have less consumption of alcohol, combusted tobacco, cannabis, and non-medical prescription drugs and greater reduction in severity of nicotine dependence as assessed with the ECDI during the treatment and follow-up periods than those in the placebo or EUC groups.

PILOT STUDY 2020P002774-Pilot - NCT04602494

In 2021, during the national recall of varenicline in the US, the FDA provided temporary authorization for importation of apo-varenicline from the Canadian company, Apotex. A pilot vaping cessation trial was conducted using apo-varenicline or identical placebo in 4 study participants who met inclusion and exclusion criteria below except that the age range was limited to 18-25. In this pilot trial, all study procedures listed below were piloted, including the emocha platform for study medication adherence and daily report of vaping behavior and adverse effects and the novel, brief lay-counselor behavioral vaping cessation intervention.

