| Assessments | Enrollment | BL (Wk0) | Wk 1-3 | Wk 4 | Wk 5-7 | Wk 8 | Wk 9-11 | Wk 12 | Wk 16 | Wk 20 | Wk 24 |
| Screening | |   | - | | - | - | - | | - | - | |
| Consent | Х | - | - | - | - | - | - | - | - | - | - |
| Demographics, Vaping history | Х | - | - | - | - | - | - | - | - | - | - |
| Primary outcomes | | | | | | | | | | | |
| Salivary cotinine*** | Х | Х | Х | Х | Х | Х | х | Х | Х | Х | Х |
| Timeline followback (TLFB) | х | Х | Х* | Х | Х* | Х | Х* | х | х | Х | Х |
| Daily vaping exposure y/n via REDCap (for those not randomized to EUC) | - | Х | Х | х | х | х | Х | Х | - | - | - |
| Secondary/exploratory outcomes | ; | | | | | | | | | | |
| MNWS | Х | Х | Х | Х | Х | Х | Х | Х | - | - | - |
| QVC | Х | х | х | Х | Х | Х | х | х | - | - | - |
| MASQ-D30 | х | Х | - | Х | - | Х | - | х | х | Х | Х |
| NAEI | х | х | - | х | - | х | - | х | х | Х | Х |
| Adverse events | - | х | Х | Х | Х | Х | х | х | х | Х | Х |
| Other biomarkers | | | | | | | | | | | |
| Urine NNAL | - | х | - | - | - | - | - | х | - | - | Х |
| ТНС-СООН | - | х | - | - | - | - | - | х | - | - | Х |
| СО | х | - | - | - | - | - | - | - | - | - | - |
| Pregnancy test | х | х | - | х | - | х | - | х | - | - | - |
| Drug screen | х | х | - | х | - | х | - | х | х | х | х |
| Vital signs | х | х | - | х | - | х | - | х | - | - | - |
| Height and weight | х | - | - | - | - | - | - | - | - | - | - |
| Saliva (genetics) | х | - | - | - | - | - | - | - | - | - | - |
| Descriptions, effect modifiers, cov | variates | | | | | | | | | | |
| Medical History | х | - | - | - | - | - | - | - | - | - | - |
| Concomitant medications | х | х | х | х | х | х | х | х | х | х | Х |
| ECDI | х | - | - | - | - | - | - | х | - | - | Х |
| AUDIT | х | - | - | - | - | - | - | х | - | - | Х |
| CUDIT | х | - | - | - | - | - | - | х | - | - | Х |
| BRIEF-SR | х | - | - | - | - | - | - | х | - | - | - |
| C-SSRS | Х | - | - | - | - | - | - | - | - | - | - |
| WTAR | Х | - | - | - | - | - | - | - | - | - | - |
| UPPS-P | Х | - | - | - | - | - | - | - | - | - | - |
| CHRT | - | Х | - | Х | - | Х | - | Х | -X | -X | -X |
| Flavor preferences | х | - | - | - | - | - | - | - | - | - | - |
| Peer and family influence on vaping | х | - | - | - | - | - | - | - | - | - | - |
| PATH Instruments: Vaping and substance use history, modified WTQ, MTQ | Х | - | - | - | - | - | - | - | - | - | - |
| YSS | - | - | - | - | - | - | - | Х | - | - | - |

| TIQ | - | х | Х | Х | Х | х | х | х | - | - | - |

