Neuropsychiatric Adverse Events Interview (NAEI)³⁶ is a semi-structured interview designed to systematically assess the presence and severity of specific neuropsychiatric symptoms and will be administered at enrollment, baseline and at each assessment visits. This instrument will be asked in regards to the past six months (at enrollment) and since the last assessment visit (all other timepoints).

Adverse Events will be assessed weekly by the study staff via REDCap during the treatment phase and then monthly during assessment visits to assess the tolerability of the study procedures.

Concomitant Medications will be assessed by self-report at each visit.

Peer Network Stability: At baseline, V12, and 3-month follow-up, participants will be asked to list and rank up to 10 friends in order of closeness, using a modified version of the "concentric circles of closeness" sociometric measure used in. ^{80, 82} Participants will generate their friends' names by free recall to ensure (1) friends included in the study could come from any context and (2) participants designated only individuals whom they truly considered to be friends.⁸¹ A friendship network instability index will be created by calculating the absolute value of the sum of each peer's rank change divided by the total number of peers the adolescent listed at the consecutive time points to account for differences in network sizes.⁷⁹

Modified Mental Health Youth Satisfaction Survey(YSS)⁶⁹ is a 26-item self-rated survey of youth perception of services in 5 domains: access to services; appropriateness of services; cultural sensitivity; participation; and treatment outcome whose internal consistency ranges from 0.70 - 0.94. It has been widely used in state mental health systems to assess youth satisfaction with services and will be given at week 12 to assess participant satisfaction with the intervention.

The Impulsive Behavior Scale (UPPS-P) – Short⁷⁰ will be given at enrollment to assess five components of impulsivity, including sensation seeking, lack of premeditation, lack of perseverance, negative urgency, and positive urgency. Scores on many of these factors have been shown to relate to risk behavior.

The Wechsler Test of Adult Reading (WTAR)⁷¹ will be used to assess speech and dictation and derive an estimated IQ at enrollment.

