Hypothesis 2.1: We will use a linear model applied separately to repeated, continuous weekly assessments of nicotine withdrawal symptoms, craving, and negative mood symptoms. The linear model will be estimated using generalized estimating equations (GEE), providing estimates and standard errors robust to violations of distributional assumptions (e.g., normality), and heteroscedasticity. The model will be applied to the summed scores at each time point per subject. The analysis will be intent-to-treat with missing data imputed per the method specified above. The key confirmatory effect will be a dummy-coded contrast comparing placebo (coded as 0) against varenicline (coded as 1). Exploratory analyses will also be conducted to evaluate varenicline versus EUC and placebo versus EUC. The model will include covariates for a) change over time (two terms encoding linear and quadratic trends), b) baseline levels of the given outcome, as well as c) sex, environment (secondary school versus post-secondary school), and severity of nicotine dependence. Covariates will be standardized (mean-centered and scaled by the standard deviation). P-values will be adjusted to avoid multiple comparison issues using the Benjamini-Hochberg method.

Hypothesis 2.2: We will conduct a Fisher's exact test differences by randomized group in the number (%) of participants who endorse an AE at least once in the 12-week treatment period. We will evaluate frequent AEs (e.g., that occur in at least 5% of the participants at any point between weeks 1 through 12 of the trial).

Sensitivity analyses: We will conduct 3 sensitivity analyses to examine the robustness of our conclusion for efficacy.

- 1. We will test whether our conclusion on efficacy is robust to the inclusion/exclusion of the 3 covariates (biological sex, environment [secondary school vs. post-secondary school], and nicotine dependence severity) we therefore will rerun the analyses without the 3 covariates and examine whether the pooled estimate for the contrasts between varenicline, placebo, and/or EUC changes in sign and significance.
- 2. We will test whether our conclusion on efficacy is robust to the approach for imputation of missing data, examining whether the pooled estimate for the contrasts between varenicline, placebo, and/or EUC changes in sign and significance.
 - a. We will rerun the adjusted (i.e., with covariates) models on the observed data only.

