The goal of this project is to test whether varenicline, the most effective treatment known for addiction to smoked tobacco, helps adolescent non-smokers who have developed nicotine dependence to quit vaping nicotine. This may benefit other adolescent nicotine vapers in the future and increase abstinence rates in this population by informing clinicians and adolescents who vape and their families of effective treatment options for nicotine vaping cessation. Given the prevalence of vaped nicotine use among adolescents who never smoked is rising more rapidly than any prior known drug, putting them at elevated risk for nicotine dependence, tobacco smoking, other drug use, and direct negative health effects of vaping, we believe that the few potential risks to participants in this research are outweighed by the potential benefits

IX. MONITORING AND QUALITY ASSURANCE

a. Independent monitoring of source data

All data management will be conducted in the offices of the PI at the MGH Center for Addiction Medicine (CAM) in Boston. Standard REDCap data collection forms for all proposed clinical rating scales will be used. Tablets with HIPAA compliant REDCap capability will be used to capture raw data from clinical rating scales entered by participants and study staff and self-reported substance use behavior. A study database will be designed by the PI and the data manager and maintained by the PI, the data manager and the research coordinators. The data manager will review the data weekly. Access to the database is restricted by password. The database will be protected by nightly backup on MGH servers. All data will be stored safely for at least 5 years after study completion.

b. Safety monitoring

An independent Data and Safety Monitoring Board (DSMB) will be appointed for this study, to assess the safety of the study by determining whether there is an unacceptable level of risk due to study medication, study procedures, and whether an increased number of adverse events occur. The DSMB will be established to analyze interim results to assess the safety of the study drug at regular intervals for the duration of the study by determining whether an increased number of adverse events occur among study participants receiving drug compared to participants receiving placebo.

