The board will include a statistician, a smoking cessation expert, a pediatrician, and a psychiatrist. Each member of the DSMB will not otherwise be associated with the trial. Safety data will be reviewed by the Data and Safety Monitoring Board Data every 6 months after the recruitment period begins. The DSMB will receive summary reports on recruitment, retention and description of all adverse events and review them at each biannual DSMB

meeting. The DSMB will receive all communication with the IRB and with the FDA. Subject information provided to the board will be identified only with study IDs to protect the confidentiality of subjects. The DSMB will assess interim results to determine whether the active drug treatment is associated with substantial risk, including higher rate of adverse outcomes when compared with the placebo group.

c. Outcomes monitoring

A DSMB Report written by the chair and approved by all members will be issued to the IRB, FDA, and the NIDA Project Officer after every DSMB meeting. The report will include, but may not be limited to, a synopsis of the trials, their progress to date, characteristics of participants enrolled, retention and disposition of study participants, quality assurance issues, regulatory issues, and reports of AEs and SAEs.

Criteria for trial stopping rules: If serious adverse events occur more frequently in the active group compared to the placebo group, at a 2-tailed p value of <0.05, then the DSMB will discuss with the PI and co-investigators whether the trial should be stopped

d. Adverse event reporting guidelines

Study staff, including co-investigators, research coordinators, and data managers, will meet weekly with the PIs and the Project Director during a weekly project management meeting to review study progress, including any adverse events.

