All adverse events volunteered, observed, or solicited will be recorded in the AE CRF from the time the subject signs the informed consent up to and including Week 24. The PI will meet weekly with all study investigators to review the details of data acquisition and analysis as well as any minor problems. AEs will be assessed for each subject at every visit. All adverse events will be recorded and will include the dates of occurrence; severity; assessment of relationship to study drug; countermeasure(s); specific drug therapy used in countermeasure; and outcome. Adverse events will be reviewed by the PI who will complete an adverse event report form and submit this to the IRB within the required time frame in accordance with the IRB guidelines.

Reporting Adverse Events: The PI will report all adverse events experienced by the study subjects in accordance with HRC (Human Research Committee) guidelines to the Institutional Review board. Adverse events will also be reported by the principal investigator to the funding agency and to the FDA in accordance with IND regulations. The reporting of adverse events is the responsibility of the PIs, Drs. [name] and [name].

In case of serious adverse events (SAE's), the PI will report them within 24-hours by telephone, fax or email according to HRC guidelines, followed by a written report within 5 business days. SAEs that occur within 30 days after a subject's last dose of study medication that are categorized as definitely, probably or possibly relate¹d to the study will be reported to the HRC and FDA. An annual report will be submitted to the HRC and the FDA of the progress of the trial. This will include individual study information and information on safety reports from the previous year.

X. REFERENCES

- Johnston, L. D. et al. Monitoring the Future National Survey Results on Drug Use, 1975-2018: Overview, Key Findings on Adolescent Drug Use. (Institute for Social Research, 2019).
- Wang, T. W. *et al.* Tobacco Product Use and Associated Factors Among Middle and High School Students — United States, 2019. *MMWR Surveill. Summ.* 68, 1–22 (2019).
- 3. Barrington-Trimis, J. L. & Leventhal, A. M. Adolescents' Use of 'Pod Mod' E-Cigarettes Urgent Concerns. *The New England journal of medicine* **379**, 1099–1102 (2018).
- 4. Kong, G. & Krishnan-Sarin, S. A call to end the epidemic of adolescent E-cigarette use. *Drug and Alcohol Dependence* **174**, 215–221 (2017).

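### Hypothesis 2.2 covers adverse event incidence and severity through follow-up, but its planned analysis covers only incidence in weeks 1-12

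*Combined protocol and SAP*

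**What the plan says.** Section II, Hypothesis 2.2, under the secondary safety aim, predicts "no greater incidence or severity of adverse events (AE) compared with those assigned to placebo or EUC during treatment and follow-up" for participants assigned to varenicline.

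Section VI, under Hypothesis 2.2, plans a Fisher's exact test by randomized group on the number and percentage of "participants who endorse an AE at least once in the 12-week treatment period". It adds an evaluation of frequent AEs, with 5% of participants in weeks 1-12 as the example threshold. Nothing else in Section VI is labeled as an analysis of this hypothesis.

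The data go further than the analysis. Section IX.d says that AEs "will be recorded in the AE CRF from the time the subject signs the informed consent up to and including Week 24", and that each record "will include the dates of occurrence; severity; assessment of relationship to study drug". The Time and Events Table in Section V.a places the NAEI under "Secondary/exploratory outcomes" and schedules it to week 24. Section V.f describes it as a "semi-structured interview designed to systematically assess the presence and severity of specific neuropsychiatric symptoms".

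**The concern.** The hypothesis and its analysis do not match. The hypothesis speaks of how severe AEs are as well as how many participants have them, and of follow-up as well as treatment. The test counts participants with at least one AE during treatment. Someone with one mild headache and someone with repeated severe vomiting count the same, and an AE that starts in week 14 does not count.

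What is at stake is the reading of a null result. If the Fisher test is non-significant, a report could say that Hypothesis 2.2 was supported when severity and the follow-up period were never compared. If severity is examined only after unblinding, the cut-off and the window will be chosen with the data in view. The trial enrolls from age 16 a drug that Section VII.i notes is not approved under 18, and Section VI argues that a large benefit is needed to justify the risk of medication. The safety conclusion should therefore not claim more than was tested.

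**Working it through.** The documents give no figure on this point, so there is none to reproduce. The main check is textual.

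**Coverage of Hypothesis 2.2**

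| Element | Hypothesis (Section II) | Analysis (Section VI) | Data collected |
|---|---|---|---|
| Incidence, weeks 1-12 | yes | yes | yes |
| Severity, weeks 1-12 | yes | no | yes, AE CRF |
| Incidence, weeks 13-24 | yes | no | yes, AE CRF with dates |
| Severity, weeks 13-24 | yes | no | yes, AE CRF with dates |

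Two attributes times two periods give four cells; the plan fills one. None of the three follow-up visits (weeks 16, 20 and 24) enters an AE analysis. Reading the frequent-AE sentence as one Fisher test per AE term does not change this, because each would still be a yes/no count in weeks 1-12.

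**Other text that might fill the gap**

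- Hypothesis 2.1 models weekly scores for withdrawal, craving and negative mood. It does not address AE severity.
- The three sensitivity analyses concern efficacy only.
- The general sentence on safety analyses in Section VI separates the pilot drug source from the main one. It adds no endpoint or window.
- The DSMB review (Section IX.b and c) is taken up under the objection.

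**Illustration, with assumed rates**

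The documents give no any-AE or moderate-or-severe AE rates, so the rates below are assumptions. Sample size: up to 240 randomized 1:1:1 (Sections II and IV.c), so 240/3 = 80 per arm at most. Tests are two-sided Fisher at 0.05. Intervals are Newcombe's: with d = p1 - p2 and Wilson limits (l, u) for each arm, lower = d - sqrt[(p1 - l1)² + (u2 - p2)²] and upper = d + sqrt[(u1 - p1)² + (p2 - l2)²].

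1. Any AE, 64/80 in both arms. Wilson limits 0.6995 to 0.8730. Half-width = sqrt[(0.8 - 0.6995)² + (0.8730 - 0.8)²] = 0.124. Difference 0, 95% CI -12.4 to 12.4 points, p = 1.0.
2. Moderate-or-severe AE, 20/80 v 8/80. Wilson limits 0.1681 to 0.3548 and 0.0515 to 0.1851. Lower = 0.15 - sqrt[(0.25 - 0.1681)² + (0.1851 - 0.10)²] = 0.032. Upper = 0.15 + sqrt[(0.3548 - 0.25)² + (0.10 - 0.0515)²] = 0.266 (0.2655 before rounding). Difference 15 points, 95% CI 3.2 to 26.6, p = 0.021.
3. By exact binomial enumeration, when any-AE rates are equal at 40% to 90%, the planned test flags varenicline as worse in 1.4% to 1.7% of trials, whatever the difference in severity.
4. A moderate-or-severe comparison has this power for a true excess on varenicline:

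| Placebo rate | 5% | 10% | 15% | 20% | 30% | 40% |
|---|---|---|---|---|---|---|
| +15 points | 79% | 65% | 56% | 50% | 44% | 41% |
| +10 points | 48% | 35% | 29% | 25% | 21% | 19% |

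**What an added comparison could not do**

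- Uncommon events at 80 per arm: power is 5% for 4% v 1%, 11% for 6% v 2% and 16% for 8% v 3%. With 0/80 events, the upper limit is 1 - 0.025^(1/80) = 4.5%.
- Late effects: the only late rate in the protocol is irritability and sleep disturbance after abrupt discontinuation, in up to 3% of patients (Section VII.i). Take 3% v 0%. Against 0 events, 5 on varenicline give p = 0.058 with 68 per arm (0.85 × 80, assuming 85% retention) and p = 0.059 with 80, so 6 are needed. The chance of 6 or more is 1.6% with 68 per arm and 3.3% with 80.

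**The case against.** The strongest reply is that safety is already compared by arm. Section IX.b has the DSMB assess whether "an increased number of adverse events occur among study participants receiving drug compared to participants receiving placebo", and Section IX.c sets a trigger "If serious adverse events occur more frequently in the active group compared to the placebo group" at two-tailed p < 0.05. A reader might infer from the point above that the trial has no by-arm safety review beyond the Fisher test. The documents do not support that. But the DSMB review is interim monitoring, it compares drug with placebo and not with EUC, and seriousness is not graded severity. It does not supply the final analysis of Hypothesis 2.2.

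Second, a reader might infer that the protocol expects worse AEs on varenicline. It does not say so. Section VII.i reports that the incidence of nausea and vomiting rises with exposure, which the planned test can address. It also reports that all AEs but one in the adolescent pharmacology work were mild or moderate, and that a 307-participant adolescent trial found no difference in tolerability. The case for analyzing severity is that the hypothesis names it.

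Third, it is tempting to add the suicidality scale (CHRT-SR) as an unanalyzed safety outcome. The Time and Events Table puts it among descriptions, effect modifiers and covariates, and Section V.f uses it to supplement AE queries. A missing by-arm test of it is not an inconsistency. The NAEI is different, because the table lists it as an outcome. Even so, Hypothesis 2.2 names neither instrument. Section IX.d also records solicited AEs, so findings from either could reach the any-AE count indirectly.

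Fourth, the low power for late or uncommon events is conceded. It argues for reporting estimates with intervals and against adding confirmatory tests.

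**Conclusion.** The mismatch stands. As written, the plan addresses AE incidence in weeks 1-12, one of the four combinations in Hypothesis 2.2, and is silent on severity and on weeks 13-24. A non-significant result cannot support the hypothesis as stated. This follows from the text alone.

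The size in numbers is illustrative. It rests on assumed rates and the maximum of 80 per arm, and shows only that an any-AE test is blind to a difference confined to severity. Nothing in the documents shows that such a difference, or a late one, is likely. This is a secondary aim with interim oversight in place, so the point should be put right before the analysis but does not threaten the design.

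**What to change.** Add to Hypothesis 2.2 in Section VI a by-arm table from the AE CRF:

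- n (%) with any AE and n (%) with any moderate-or-severe AE, naming the grading scale, which the protocol does not state.
- Risk difference with 95% CI for varenicline v placebo and for varenicline v EUC, since the hypothesis names both. Note beside the EUC contrast that only the drug and placebo arms have the daily platform for reporting tolerability, although staff query AEs weekly.
- Weeks 1-12, and separately AEs with onset in weeks 13-24, with the number assessed in each. Do not compare the two periods with each other, because AE queries go from weekly to monthly.

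For the NAEI, report n (%) by arm with a new or worsened symptom in the same periods, as an estimate. Its look-back is six months at enrollment and since the last assessment visit thereafter, so count a symptom only if it exceeds the worse of the enrollment and baseline ratings.

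Otherwise, narrow Hypothesis 2.2 and its conclusion to AE incidence in weeks 1-12.

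The first option costs one paragraph and two tables from data already collected, with no new visits or participants. Its drawback is a few more descriptive comparisons with wide intervals (about 12 points either side at 64/80 v 64/80) and little power for uncommon events, including the discontinuation symptoms. The second option costs one sentence.
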